1. STUDY OBJECTIVES AND ENDPOINTS

1.1. Primary and Secondary Study Objectives and Endpoints

The primary and secondary study objectives and endpoints are as follows:

Objectives	Endpoints

The primary objective of the study is to estimate the treatment effect of fremanezumab administered subcutaneously in reducing pain in adult patients with Fibromyalgia (FM).
	
The primary efficacy endpoint is the change from baseline to week 12 in the weekly average of the daily average PI-NRS score over the past 24 hours.

A secondary objective is to evaluate the effect of fremanezumab on other efficacy measures, including pain, quality of life, sleep, fatigue, improvement in health, physical functioning, and mood.
	
The secondary efficacy endpoints are as follows:
 
 • change from baseline to week 12 in the individual components of the Fibromyalgia Impact Questionnaire Revised (FIQR): symptom subscore, impact subscore, and functional subscore score • responder rate of the Patient Global Impression of Change (PGIC) rating (percentage of patients much improved or very much improved) at week 12 • the percentage of patients who experience a $\geq 30\%$ reduction in the weekly average of the daily average PI-NRS score at week 12 • the percentage of patients who experience a $\geq 50\%$ reduction in the weekly average of the daily average PI-NRS score at week 12 • change from baseline to week 12 in the weekly average of the daily worst PI-NRS score over the past 24 hours • change from baseline to week 12 in the Patient-Reported Outcomes Measurement Information System (PROMIS) Sleep Disturbance Short Form (SF) 8a score • change from baseline to week 12 in the PROMIS Physical Function SF12a score • change from baseline to week 12 in the PROMIS Fatigue SF8a score

Objectives	Endpoints
	
 • number (%) of patients who did not complete the treatment (Kaplan-Meier Survival Analysis) due to lack of efficacy

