  MODELEFFECTS ESTIMATE;  
  STDERR STDERR;  
RUN;  
ODS OUTPUT CLOSE;
```

Where `ESTIMATE` and `STDERR` are LS mean and standard error from Step 4.

(b) For treatment difference, treatment difference CI and p-values

```
PROC SORT DATA= DIFF;  
  BY WEEK TRT01PN _TRT01PN _IMPUTATION_ ;  
RUN;  
  
ODS OUTPUT PARAMETERESTIMATES= DIFF_O;  
PROC MIANALYZE DATA= DIFF;  
  BY WEEK TRT01PN _TRT01PN;  
  MODELEFFECTS ESTIMATE;  
  STDERR STDERR;  
RUN;  
ODS OUTPUT CLOSE;
```

The observed data (ie, without imputation for missing data) will be summarized using descriptive statistics by analysis weeks (baseline, weeks 1 to 16).

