For analysis purpose, a dichotomous scale of 'Yes' or 'No' will be derived. Scale "much improved" or "very much improved" will be considered improved (Yes), and all other non-missing responses will be considered not improved (No). Missing category will be presented as appropriate.

The response variable (yes or no) at week 12 will be analyzed using a logistic regression model with the treatment, age group at FM onset, and sex as explanatory factors. Missing category will not be included.

SAS code is:

```
ods output diffs = dif LSMeans = ls;  
PROC GENMOD DATA =name;  
CLASS TRT01PN STRATAR SEX;  
MODEL AVALCAT1 = TRT01PN STRATAR SEX / DIST=BIN TYPE3;  
LSMEANS trt01pn/exp DIFF CL;  
RUN;  
ods output close;
```

Statistical Analysis Plan

```
data ls;
set ls;
** p = estimated response rate;
p = logistic(estimate);
p_l = logistic(Lower);
p_u = logistic(Upper);
run;
```

Where AVALCAT1 denotes the responses with ‘yes’ for improved and ‘no’ for not improved.

In addition, the PGIC data will be summarized as a categorical variable using descriptive statistics for all visits, including missing category as appropriate.

6.3.3. Percentage of Patients Who Experience a $\geq 30\%$ or $\geq 50\%$ Reduction in the Weekly Average of the Daily Average PI-NRS Score at Week 12

The weekly average of the daily average PI-NRS score with missing data imputation from the 500 imputed data sets derived as described in steps 1 to 3 of Section 6.2.2 will be used to calculate the pain intensity reduction (%) from baseline in the weekly average of the daily average PI-NRS score using formula [2].

$$\frac{\text{baseline value} - \text{postbaseline value}}{\text{baseline value}} \times 100\% \quad [2]$$

The percentage of patients who experience $\geq 30\%$ reduction and $\geq 50\%$ reduction in the weekly average of the daily average PI-NRS score at week 12 will be analyzed using a generalized estimating equation (GEE) method where the dependent variable is $\geq 30\%$ reduction (Yes/No) or $\geq 50\%$ reduction (Yes/No), respectively, [REDACTED]

SAS code for GEE model:

```
ods output LSMeans = ls;
PROC GENMOD DATA =name;
  BY _IMPUTATION_;
  CLASS SUBJID TRT01PN WEEK STRATAR SEX;
  MODEL AVALCAT = BASE TRT01PN WEEK STRATAR SEX
          TRT01PN*WEEK/ DIST=BIN TYPE3;
  REPEATED SUBJECT = SUBJID / TYPE = AR(1);
  LSMEANS trt01pn*week/exp DIFF CL;
RUN;
ods output close;
```

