Where AVALCAT denotes the responses with ‘yes’ for $\geq 30\%$ or $\geq 50\%$ or ‘no’ for $< 30\%$ or $< 50\%$ pain intensity reduction, respectively.

The 500 sets of results from above analyses will be combined using Rubin’s formulae (PROC MIANALYZE).

```
PROC SORT DATA= LS;
```

Statistical Analysis Plan

```

    BY WEEK TRT01PN _IMPUTATION_ ;
RUN;

ODS OUTPUT PARAMETERESTIMATES= LSM_O;
PROC MIANALYZE DATA= LS;
    BY WEEK TRT01PN;
    MODELEFFECTS ESTIMATE;
    STDERR STDERR;
RUN;

DATA LSM_O;
    SET LSM_O;
    EXPESTIMATE = EXP(ESTIMATE);
    P = 100*EXPESTIMATE/(1 + EXPESTIMATE);
    P_LL = 100*EXP(LCLMEAN)/(1 + EXP(LCLMEAN));
    P_UL = 100*EXP(UCLMEAN)/(1 + EXP(UCLMEAN));
RUN;

```

In addition, the mean percentage of reduction and its associated 95% CI will be reported by week.

A plot of percentage of improvement versus percentage of patients meeting the improvement level at week 12 will be presented based on observed data and missing data at week 12 will be deemed as pain intensity increased from baseline. The x-axis representing percentage of improvement will be from ≥ 0 to 100% by an increment of 10%, ie., the x-axis will be at cutoff points $\geq 0\%$, $\geq 10\%$, $\geq 20\%$, ..., $\geq 90\%$ and 100% while y-axis will be percent of patients meet the cutoff points. The percentage of improvement will be calculated using formula [2].

6.3.4. Change From Baseline to Week 12 in the Weekly Average of the Daily Worst PI-NRS Score Over the Past 24 Hours

The weekly average of the daily worst PI-NRS score over the past 24 hours will be analyzed in a manner analogous to the primary endpoint as described in Section 6.2.2. The dependent variable is the change from baseline in the weekly average of the daily worst PI-NRS scores. The covariate will be baseline average of the daily worst PI-NRS scores.

6.3.5. Change From Baseline to Week 12 in the Patient-Reported Outcomes Measurement Information System Sleep Disturbance Short Form 8a Score

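### The SAP 6.3.3 responder code does not save or pool the treatment differences it requests, and the unredacted text names no pooled dose-versus-placebo contrast with CI or p-value

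*SAP*

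**What the plan says.** SAP 1.1 lists two responder endpoints at week 12, each worded as "the percentage of patients who experience a" given reduction (at least 30%, at least 50%) in weekly average pain. The objective they serve is to evaluate the effect of fremanezumab.

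SAP 6.3.3 analyses them by GEE in each imputed data set. The model step contains "LSMEANS trt01pn*week/exp DIFF CL", so differences are requested. The output line is "ods output LSMeans = ls", so only the arm-by-week means are stored. The prose then states: "The 500 sets of results from above analyses will be combined using Rubin’s formulae". The only pooling block reads the stored means, runs "BY WEEK TRT01PN", and back-transforms the result to arm percentages with limits. Beyond that, 6.3.3 promises a mean percentage of reduction with a CI by week, and a descriptive plot. The sentence describing the analysis is blacked out partway through.

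Protocol 9.6.4.3 gives the model terms for these endpoints and names no odds ratio, difference, CI or p-value.

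**The concern.** An effect of treatment is a comparison with placebo. The displayed code computes that comparison in every imputation, discards it, and carries only the separate arm results forward. Two arm percentages with their own intervals do not give an interval or test for the difference between them. A programmer who follows the code would deliver tables with no inferential comparison for two secondary endpoints. Anyone wanting one would have to construct it later, possibly after unblinding, or judge informally from the arm intervals.

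**Working it through.** **Plan's own figure.** The documents give no figure for the responder endpoints. Their only sizing figure (SAP 2.4) is at least 90% probability that the 95% CI half-length for the pain difference is below 0.74, with SD 2.2 and 80 per arm. The half-length is t(0.975,158) × s × √(2/80), so the requirement is s < 0.74/(1.975 × 0.1581) = 2.370. Then P(χ²₁₅₈ < 158 × (2.370/2.2)²) = 0.918. The figure is reproduced, but it has no bearing on this point.

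**Code compared across sections.**

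| SAP section | Endpoint | Differences saved | Differences pooled | Readable text promises a contrast with CI and p-value |
|---|---|---|---|---|
| 6.2.2 | Primary pain score | Yes, same week only | Yes, Step 5(b) | Yes |
| 6.3.1 | FIQR | Yes, same visit only | Not imputed, none needed | Yes |
| 6.3.2 | PGIC responder | Yes | Not imputed, none needed | No |
| 6.3.3 | 30%/50% responders | No | No | No (part redacted) |

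The 6.2.2 pooling has two blocks: (a) for LS means, and one headed "b) For treatment difference, treatment difference CI and p-values". Section 6.3.3 reproduces the first and has no counterpart to the second. The PGIC output line, "ods output diffs = dif LSMeans = ls", shows the differences being kept for the other binary endpoint.

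**What is produced.** Per week, 3 arm means and 0 contrasts are pooled. At week 12 the missing contrasts are 2 endpoints × 2 doses = 4.

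**What can be recovered from pooled arm means.** Rubin's point estimate is an average, so it is linear: the pooled log odds ratio equals the pooled active mean minus the pooled placebo mean. The variance is Var(A) + Var(P) − 2Cov(A,P). The stored output gives the first two terms only. The covariance is not zero, because all arm means from one model share the estimated covariate effects.

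**Illustration with assumed inputs.** This is one simulated data set: a logistic model at a single week (not the GEE), 80 per arm, 20% missing, 200 imputations, adjustment for sex, age group and baseline, 10% of patients in one sex category.

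- Pooled arm means (SE): placebo −0.722 (0.342), first dose −0.954 (0.355), second dose −0.766 (0.337).
- By subtraction: −0.954 + 0.722 = −0.232 and −0.766 + 0.722 = −0.044. Pooling the differences directly gives the same values.
- SE from pooling the differences: 0.345 and 0.365.
- SE if the arms are treated as independent: √(0.342² + 0.355²) = 0.493 and √(0.342² + 0.337²) = 0.480.
- Ratios: 0.493/0.345 = 1.43 and 0.480/0.365 = 1.32, so the SE is about 43% and 32% too large.

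**Why the same-week restriction is needed.** Three arms × 12 weeks = 36 cells, and 36 × 35/2 = 630 pairwise differences per imputation. Only 2 × 12 = 24 are same-week dose-versus-placebo contrasts, 2 of them at week 12. Without a filter, each week-and-arm-pair group holds 12 rows per imputation, one of them same-week. Over 500 imputations, 12 × 500 = 6,000 rows would be pooled where 500 are wanted.

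**The case against.** The strongest reply is that the plan may well contain the comparison. The sentence defining the analysis is blacked out, and in 6.3.1 the promise of a difference with CI and p-value stands between the model description and the code, which is where the 6.3.3 redaction lies. The matching protocol sentence continues with model terms, but nothing shows that the hidden text holds only those. DIFF is requested, and the sentence on combining the 500 sets of results is not limited to arm means. This stands: a reader might infer that the plan provides no fremanezumab-versus-placebo estimate for these endpoints, and the documents do not support that. A point odds ratio also follows by subtraction.

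What survives is the code. The output and pooling statements are visible and cannot yield a pooled contrast with its precision. If the redacted text promises one, prose and code disagree and the code still needs changing.

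Two further replies have weight. The PGIC comparator is only partial, since 6.3.2 saves the differences but neither describes nor uses them. And these are secondary endpoints of a proof-of-concept study ended for futility, with no multiplicity adjustment (SAP 2.5.1 and 7). That limits the consequence. It does not remove the need for an interval showing which effects remain compatible with the data.

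**Conclusion.** The point holds for the displayed code and the readable text. As written, 6.3.3 delivers no valid pooled SE, CI or p-value for four week-12 dose-versus-placebo contrasts, while the primary and FIQR analyses do deliver theirs. It looks like an omitted block rather than a decision not to compare. It should be corrected, but it does not touch the primary analysis, or the worst-pain endpoint, which follows the primary method (6.3.4).

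The count of four comes directly from the endpoints and doses. The 43% and 32% figures rest on one simulated data set with assumed inputs; they show the direction of the error, not its size in this trial. A reader might also want to attach a fixed significance level to non-overlap of the arm intervals. That calculation assumes independent arm estimates, which means from one covariate-adjusted model are not, so no such level is claimed here.

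**What to change.** In 6.3.3:

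1. Change the output line to save both tables with the restriction used in 6.2.2 Step 4, for example `ODS OUTPUT LSMEANS=LS DIFFS=DIFF (WHERE=(WEEK=_WEEK));`.
2. Add a second MIANALYZE block on the differences, by week and arm pair (`WEEK TRT01PN _TRT01PN`), after sorting, as in 6.2.2 Step 5(b).
3. Check that each contrast runs active minus placebo, then exponentiate the estimate and limits.
4. State in the text that the week-12 odds ratio, 95% CI and p-value for each dose versus placebo will be reported for both responder definitions.

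The cost is a few lines of reused SAS and one sentence, with no new data or model. SAP 2.5.2 provides for amendments approved before database lock. Making the change then fixes the contrast before the codes are opened. Simply adding the differences table without the same-week restriction would give a wrong pooled result.

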3.4. Stopping Rules for the Study

There are no formal rules for early termination of this study. During the conduct of the study, serious adverse events will be reviewed (Section 7.1.5) as they are reported from the investigational centers to identify safety concerns.

The study may be terminated by the sponsor for any reason at any time. For example, the sponsor should terminate the study in the event of:

- new toxicological or pharmacological findings or safety issues that invalidate the earlier positive benefit-risk assessment
- discontinuation of the development of the IMP

If the whole study or specific arms of the study will be stopped, the patients that are terminated early will be followed according to Section 4.3.

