9.15. Planned Interim Analysis

A formal interim analysis for futility in this proof-of-concept study is planned after 68 patients have been enrolled; the interim analysis will be performed by an independent third party. A second interim analysis, for futility or continuation of the study, is planned after approximately 150 patients have completed the study; the interim analysis will be performed by a team, which is independent and isolated from the study team, who will be kept blinded. Details of the interim analyses will be specified in the interim analysis statistical analysis plan.

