1.4. Estimand for Primary Efficacy Endpoint

The combination of treatment policy and hypothetical strategy will be used for the primary efficacy endpoint to account for the intercurrent events. The four attributes of the estimand are defined as follows:

- A. Population:** The patients with fibromyalgia met all inclusion criteria and met none of the exclusion criteria.

Statistical Analysis Plan

The modified intent-to-treat (mITT) analysis set defined in Section 3.2 will be the primary analysis set for efficacy. In the data analyses, the treatment will be assigned based on the treatment to which patients were randomized, regardless of which treatment they actually received.

B. Variable: Change from baseline to week 12 in the weekly average of the daily average PI-NRS score over the past 24 hours.

C. Intercurrent events: Treatment discontinuation due to an adverse event, due to lack of efficacy, or due to other reasons.

For those who discontinue the treatment before week 12, no further efficacy data will be collected. The use of rescue medication for fibromyalgia pain will not be considered as an intercurrent event.

D. Population-level summary: The primary efficacy endpoint, the change from baseline to week 12 in the PI-NRS scores, will be analyzed using a Mixed Model Repeated Measures (MMRM) model with change from baseline in the weekly average of the daily average PI-NRS score over the past 24 hours at weeks 1, 2, 3, 4, 5, 6, 7, 8, 9, 10, 11, and 12 as the dependent variable, sex, age group at FM onset, week, treatment, and treatment by week interaction as fixed factors, and baseline average of the daily average PI-NRS score as a covariate. An adjustment for missing data due to adverse event or due to lack of efficacy on the PI-NRS scores will be on average return to baseline values, while due to all other reasons will be imputed assuming missing at random. With missing data imputed, each of the 500 imputed data sets will be analyzed using the MMRM model. The results from the 500 analyses will be combined using Rubin’s formulae. The least square (LS) mean estimates for the mean change from baseline to each time point, as well as the difference of the estimates between the fremanezumab and placebo group, with the corresponding standard error (SE), p-value and associated 95% confidence interval (CI) will be provided.

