2.5. Sequence of Planned Analyses

2.5.1. Planned Interim Analyses

There were two interim analyses for futility performed in this study. The details of the interim analyses were specified in separate interim statistical analysis plans. To ensure study integrity, the interim analyses were performed by an independent third party; the study team were kept blinded. The decision was made to end this study for futility following the results of the second interim analysis.

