2.5.2. Final Analyses and Reporting

This study has been early terminated due to futility. All analyses identified in this SAP will be performed after study closure. This SAP and any corresponding amendments will be approved before database lock, in accordance to SOP GBP_RD_702 (Statistical Analysis Plan).

The randomization codes will not be unblinded until this SAP has been approved, the database is locked, and the analysis populations are determined.

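### The week-12 responder curve in SAP 6.3.3 makes no exception for patients whose week 12 was not reached because the sponsor stopped the study, so any such patients would be plotted as worsened

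*SAP*

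**What the plan says.** SAP 6.3.3 plans a plot of improvement level against the percentage of patients reaching it at week 12. It is based on observed data, with the convention that "missing data at week 12 will be deemed as pain intensity increased from baseline". No reason for missingness is exempt. On the cutoffs the SAP says: "The x-axis representing percentage of improvement will be from ≥ 0 to 100% by an increment of 10" (per cent).

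The 30% and 50% responder analysis in the same section works differently. It uses "The weekly average of the daily average PI-NRS score with missing data imputation from the 500 imputed data sets". In those data sets, values missing after discontinuation for lack of efficacy or an adverse event return on average to baseline, "while due to all other reasons will be imputed assuming missing at random" (SAP 1.4; the code is in SAP 6.2.2).

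The SAP records the stop in two places: "This study has been early terminated due to futility" (2.5.2) and "The decision was made to end this study for futility following the results of the second interim analysis" (2.5.1). Protocol 9.15 says the second interim "is planned after approximately 150 patients have completed the study". Protocol 3.4 provides that, if the study or an arm is stopped, "the patients that are terminated early will be followed according to Section 4.3". None of these sections gives a stop date, the number on treatment at that date, or whether those patients completed dosing.

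**The concern.** Counting missing as failure is a reasonable convention when dropout tends to reflect treatment failure. A calendar stop by the sponsor carries no such information: a patient in week 6 when the study closes has not worsened. Under the text as written that patient fails every cutoff, while the model a few lines above imputes the same patient as missing at random.

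At stake is the accuracy of a display from which readers take the share reaching any chosen improvement level. Administrative cut-offs would pull every arm's curve down and narrow the gaps between arms. They would also move the plotted 30% and 50% points away from the modelled rates for a reason unrelated to pain.

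**Working it through.** **1. Reach of the rule.** The lowest cutoff is 0% improvement. A patient deemed to have more pain than at baseline falls below it, so fails every cutoff but stays in the denominator.

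**2. Who has no week 12.** SAP Table 2 defines analysis week 12 as the seven days before the fourth dosing day. SAP 1.4 says efficacy data are not collected after discontinuation before week 12. A patient ended within about 12 weeks of randomisation therefore has no observed value.

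**3. Plan's own figure.** The plan gives none for missing week-12 data. Its precision statement (SD 2.2, 80 per arm, half length below 0.74 with at least 90% probability) reproduces at 0.918 but does not bear on this point.

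**4. Accrual from the documents** (30.4375 days per month; counts and dates from the amendment history, the hold date from Protocol Appendix O):

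| Interval | Patients | Days | Per month |
|---|---|---|---|
| 25 June 2020 to 10 Aug 2021 | 153 − 68 = 85 | 411 | 6.3 |
| 16 June 2020 to 10 Aug 2021 | 85 | 420 | 6.2 |
| 22 July 2019 to 10 Aug 2021 | 153 | 750 | 6.2 |
| 22 July 2019 to 26 Mar 2020 (assumes all 68 were in by the hold) | 68 | 248 | 8.35, taken as 8.4 |
| Needed to reach 240 and finish by 31 July 2022 (not observed) | 240 − 153 = 87 | 355 − 113 = 242 | 10.94 |

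**5. Share cut off.** The following are assumed, because the documents do not give them: dropout d of 10 to 30%; lag L of 0 to 3 months from the 150th completer to the stop; enrolment at a constant rate a until the stop or 240; all ongoing patients stopped at once; share of mITT close to share of randomised.

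- Randomised at the stop: N = 150/(1 − d) + a × 112/30.4375 + a × L, capped at 240
- Randomised in the last 84 days: R = a × 84/30.4375
- Share: m = R/N

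| a | R | d = 10%, L = 0 | d = 15%, L = 1 | d = 25%, L = 1 |
|---|---|---|---|---|
| 6.2 | 17.1 | 17.1/189.5 = 9.0% | 17.1/205.5 = 8.3% | 17.1/229.0 = 7.5% |
| 8.4 | 23.2 | 23.2/197.6 = 11.7% | 23.2/215.8 = 10.7% | 23.2/239.3 = 9.7% |
| 10.94 | 30.2 | 30.2/206.9 = 14.6% | 30.2/227.7 = 13.3% | N = 251.2 exceeds 240, so (240 − 221.0)/240 = 7.9% |

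While enrolment is still open, the smallest share is R/240: 17.1/240 = 7.1% at 6.2 a month and 23.2/240 = 9.7% at 8.4. Documented rates therefore give about 7 to 12%.

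The share falls towards 0 once the cap is reached. With a = 8.4, d = 30% and L = 3, uncapped N is 214.3 + 30.9 + 25.2 = 270.4. It was 270.4 − 23.2 = 247.2 twelve weeks earlier, so nobody was randomised in the last 84 days and m = 0. If ongoing patients finished, m = 0 at any rate.

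R also counts recent patients who had already dropped out for their own reasons. A rough correction is (1 − d/2): at d = 15%, 8.3% becomes 7.7% and 10.7% becomes 9.9%.

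**6. Effect on the curve.** With the same m in each arm, a true proportion p is plotted as p(1 − m), and the gap becomes gap × (1 − m). For assumed true rates of 40% and 30%:

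| m | Plotted | Gap (points) |
|---|---|---|
| 0 | 40.0% vs 30.0% | 10.0 |
| 8% | 36.8% vs 27.6% | 9.2 |
| 12% | 35.2% vs 26.4% | 8.8 |
| 15% | 34.0% vs 25.5% | 8.5 |

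The ratio between arms does not change (36.8/27.6 = 40/30).

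**The case against.** The strongest reply is that the triggering event is not documented. The SAP says the study ended for futility and that analyses follow study closure, which also fits ongoing patients being allowed to finish. Protocol 3.4 is conditional text written before the stop. This stands, and it is why the range starts at 0. Some enrolment after August 2021 is likely: 150 completers out of 153 would need 98% completion, and SAP 6.2.4 plans a subgroup by enrolment before or after Amendment 05. Neither fact shows that enrolment was open at the stop.

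Second, the plot is descriptive and the effect is small. With about 75 per arm, the standard error of 40% minus 30% is √(0.24/75 + 0.21/75) = 7.7 points, against a shift of about 1 point. This also stands.

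Third, the plot is openly labelled as observed data with a conservative convention, and a raw proportion need not equal a covariate-adjusted model estimate. That is fair for ordinary dropout. It does not justify scoring an administrative stop as worsening.

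A reader might infer more than the documents support:

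- **A between-arm bias.** Randomisation is concurrent 1:1:1 and a calendar stop does not depend on arm, so an imbalance could arise only by chance.
- **A share of 8 to 15% as the expected figure.** Its top needs about 11 patients a month, faster than any rate documented.
- **A material problem from missed diaries.** A week is missing only if all its days are missing (SAP 6.1.3), make-up reports exist and compliance is monitored weekly.

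**Conclusion.** The point holds as a modest correction to one descriptive display. As written, the rule would plot any patient cut off by the sponsor's stop as worsened, and so departs from the missing-at-random handling of the same patients in the 30%/50% model. Whether there are such patients cannot be settled from the documents.

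If ongoing patients were stopped at once while enrolment was open, about 7 to 12% of those randomised are affected at documented accrual. The overall range is 0 to about 15%, resting on the assumed dropout and lag. The expected consequence is proportional dilution of every curve and gap.

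It would be wrong to conclude that the responder results are biased: the primary analysis and the modelled 30%/50% rates do not use this rule.

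**What to change.** Add one sentence to SAP 6.3.3. Keep the present rule for all other missing week-12 values: lack of efficacy, adverse event, withdrawal, loss to follow-up, non-compliance and any other reason. For patients whose week 12 was not reached because the sponsor ended the study, either take the week-12 value from the 500 imputed data sets already produced for the responder model, or leave these patients out of the curve's denominator and state the number per arm.

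Protocol 4.3 requires the primary discontinuation reason in the eCRF, and the SAP code already carries a reason variable. Confirm before database lock that it identifies sponsor termination.

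The cost is a few lines of programming. The downside is small: the curve is averaged over imputations, or its denominator is slightly below the full mITT. If no patient was cut off, the sentence changes nothing.
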